3.6 Coding of Events and Medications

Medical history and AE verbatim terms will be coded using the Medical Dictionary for Regulatory Activities (MedDRA) using the latest version available at the time of study commencement. Terms will be coded to the full MedDRA hierarchy, but the system organ class (SOC) and preferred terms (PT) will be of primary interest for the analysis.

Prior and concomitant medications will be coded using the World Health Organization Drug Dictionary using the latest version available at the time of study commencement. Medications will be mapped to the full WHO-DD Anatomical Therapeutic Chemical (ATC) class hierarchy, but PTs will be of primary interest in this analysis.

3.7 Treatment Groups/Treatment Sequence

TFLs will be presented by treatment arms, and for all study patients in the given analysis set, where applicable.

The following order will be used for all summary outputs (with the treatment arm displayed, as applicable to the output):

- EYP001a 200 mg QD + NA daily (N=37)
- EYP001a 200 mg QD + NA daily HBeAg+ (N=xx)
- EYP001a 200 mg QD + NA daily HBeAg- (N=xx)
- Placebo + NA daily (N=12)
- Placebo HBeAg+ (N=xx)
- Placebo HBeAg- (N=xx)
- All HBeAg+ (N=xx)
- All HBeAg- (N=xx)
- All Study Patients (N=49)

The following treatment group labels will be used for all by-participant listings:

- EYP001a 200 mg QD + NA daily HBeAg+
- EYP001a 200 mg QD + NA daily HBeAg-
- Placebo HBeAg+
- Placebo HBeAg-

4. ANALYSIS SETS

In this study 5 analysis populations are defined: Intention-To-Treat (ITT) Analysis Set, Modified Intention-To-Treat (mITT) Analysis Set, Safety Analysis Set (SAS), PK Analysis Set, the PD Analysis Set and the Per Protocol (PP) Analysis Set.

Furthermore, any additional exploratory analysis not identified in the SAP will be identified in the final CSR as exploratory post hoc analyses, including analyses for additional study populations or subgroups of interest.

4.1 Population Descriptions

4.1.1 Intention-To-Treat (ITT) Analysis Set

The ITT set will include all randomized patients, irrespective of whether a patient receives any study drug. This set will be based on randomized treatment. The ITT set will be used for the baseline, demographic summaries and efficacy summaries.

4.1.2 Modified Intention-To-Treat (mITT) Analysis Set

The mITT set will include all randomized patients, who received any amount of study drug, have a measurable baseline HBsAg assessment and a 16-week post baseline efficacy assessment. This set will be based on randomized treatment. The mITT set will be used for efficacy analyses.

4.1.3 Safety Analysis Set (SAS)

The Safety analyses set will be defined as all patients who receive at least one confirmed dose of the study drug and will be based on actual treatment received. The SAS will be used for all safety and tolerability analyses.

4.1.4 Pharmacokinetic (PK) Analysis Set (will be done by Calvagone)

The PK set will consist of all patients who received any study drug administration and that have sufficient and interpretable EYP001a concentrations data. Protocol violations and individual patient profiles will be assessed on a case-by-case basis to determine if the patient, or specific concentration values, should be excluded from the PK set.

4.1.5 Pharmacodynamic (PD) Analysis Set

All patients included in the SAS with a measurable baseline PD assessment and at least one measurable post baseline PD assessment, will be included in the PD set.

4.1.6 Per Protocol (PP) Analysis Set

The PP set is defined as the set of patients who meet the mITT set requirements and were not associated with a major protocol violation. This set will be identified before the start of the final analysis and will be used to support the analysis conducted for the primary efficacy endpoint. Patients will be analyzed based on the actual treatment received and patients with the study drug compliance of <50% will be excluded.

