6. PROTOCOL DEVIATIONS

Protocol deviations will be presented for each participant in the by-participant data listings for the enrolled set. All data will be listed by treatment group.

Prior to database lock, all protocol deviations will be reviewed by medical monitors and assigned a status of Important if qualifying as such.

Protocol deviations and important protocol deviations will be categorized as noted in the Protocol Deviation Management Plan Version 1.0 dated 2020-01-13.

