Based on the protocol clarification letter #13, the first interim analysis as described in the current EYP001-201 Study Protocol v3.0 dated 29th January 2020 corresponds to the first planned DSMC meeting and is performed on all available preliminary safety study data at the time of database snapshot (20 patients reach week 8, expected by 1st March 2021 with data cut-off point defined to be 5th March 2021.). Safety data only will be evaluated, based upon the review of the individual values (clinical significant abnormalities), descriptive statistics (summary tables, graphics) and if needed.). The term “first interim analysis” should be replaced by “DSMC Safety Review Meeting”. The “second interim analysis” corresponds to the second planned DSMC meeting covering safety review and futility analysis and is performed on all available virology, safety, PK and PD study data at the time of database snapshot when 25 patients have reached w12 (expected by 16th March 2021 with data cut-off point defined to be 15th May 2020). Safety and futility will be evaluated, based upon the review of the individual values (clinical significant abnormalities), descriptive statistics (summary tables, graphics) and on statistical analysis (futility analysis as described in section 11.5 of the study protocol). The term “second interim analysis” should be replaced by an interim analysis corresponding to “DSMC Safety and Futility Review Meeting”

There will be an additional database lock performed on all patient visits to Week 16 / Visit 9 for all randomised patients. All patients will be unblinded following database lock. Novotech Biostatistician will convert the datasets to CDISC format. Novotech data management will provide ENYO with raw data and Biostatistician will provide ENYO with CDISC converted datasets.

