16.2 Final Analysis (End of Study)

The final analysis will be conducted after all participants have completed the study (at the end of the study), the clinical database has been hard locked, the analysis populations have been approved and the study has been unblinded.

The final analysis will be based on the final version of the SAP. Any deviations from the planned analysis will be documented in the CSR.

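### The SAP allows judgement-based per-protocol exclusions for the Week 16 primary endpoint to be decided after all patients have been unblinded

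*SAP*

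**What the plan says.** SAP 4.1.6 builds the PP set from the mITT set. It keeps patients who "were not associated with a major protocol violation" and adds that "patients with the study drug compliance of <50% will be excluded". The set "will be used to support the analysis conducted for the primary efficacy endpoint". Its only timing rule is "This set will be identified before the start of the final analysis"; Protocol 11.2.3 says the same.

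SAP 16.2 puts the final analysis at the end of the study, once "the clinical database has been hard locked, the analysis populations have been approved and the study has been unblinded".

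SAP 16.1 introduces an earlier event: "There will be an additional database lock performed on all patient visits to Week 16 / Visit 9 for all randomised patients". It continues: "All patients will be unblinded following database lock". The sponsor then receives the raw data and the CDISC-converted datasets.

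On deviations, SAP 6 says: "Prior to database lock, all protocol deviations will be reviewed by medical monitors and assigned a status of Important if qualifying as such". Categories follow a Protocol Deviation Management Plan dated 13 January 2020, which is not among the documents.

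SAP 3.3 runs the primary-endpoint model six times: on ITT, mITT and PP, each with and without multiple imputation. Protocol 11.3.3.1 makes ITT primary and the other two sets sensitivity analyses.

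**The concern.** A PP set is useful only if its exclusions do not depend on the outcome. The usual safeguard is to fix membership while everyone who decides it is blinded. Here the SAP sets its deadline by the end-of-study analysis, while the primary endpoint is read at Week 16 and the codes for all patients are opened soon after that. In the interval, up to and beyond Week 40, someone deciding whether a deviation was major could know both the arm and the HBsAg change of the patient concerned.

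At stake is the credibility of two of the six planned runs. If they agree with the ITT result, a critic can say that the exclusions were chosen with the answer in view, and the SAP offers no rule to rebut that.

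**Working it through.** **Timing.**

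| Step | Place in the SAP | When |
|---|---|---|
| Week 16 HBsAg (primary endpoint) collected | 2.3.1 | Week 16 |
| Lock of all visits to Week 16, all randomised patients | 16.1 | after the last Week 16 visit |
| All patients unblinded, data to the sponsor | 16.1 | after that lock |
| Deviations rated by medical monitors | 6 | before a lock that is not named |
| PP set identified | 4.1.6 | any time up to the final analysis |
| Populations approved | 16.2 | before the final analysis, listed next to the final hard lock |

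The PP deadline falls after the unblinding. Nothing in either document requires PP membership to be fixed blind, or says that the people who settle it stay blinded after Week 16. Protocol 5.9 keeps site personnel and patients blinded throughout, but names neither the medical monitors nor the sponsor.

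**How much is open to judgement.** ITT membership (randomised), the mITT conditions (dosed, measurable baseline HBsAg, a 16-week assessment) and the 50% compliance cut follow rules. The major-violation criterion does not: SAP 4.1.6 uses that term, SAP 6 uses an Important status, and the SAP does not map one to the other.

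**Scale. Inputs.** SD 1.08 in both arms, effect -0.9, one-sided alpha 0.05, power 80%, 3:1 allocation as 37:12 (SAP 2.4 and 2.5); about 25 randomised when enrolment was suspended (SAP 15). The 19:6 split is an assumption from 3:1; the documents do not give the actual split.

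1. Check of the plan's own figure. Control arm n = (1 + 1/3) × [1.08 × (1.645 + 0.842)/0.9]² ≈ 11.9, a total of about 47.5, or 48 after rounding up to 12 controls, against 49 stated. Power at 37:12 by the noncentral t is 79.6% against 80%. The inputs reproduce the plan.
2. Standard error of the difference = 1.08 × √(1/n_E + 1/n_C).
   - 37:12: 1.08 × √(1/37 + 1/12) = 0.359
   - 19:6: 1.08 × √(1/19 + 1/6) = 0.506
3. Removing one patient who lies d from the arm mean shifts that mean by d/(n − 1). With d = 1.08 in the placebo arm:
   - 12 patients: 1.08/11 = 0.098 log10, or 0.098/0.359 = 0.27 standard errors
   - 6 patients: 1.08/5 = 0.216 log10, or 0.216/0.506 = 0.43 standard errors
4. Upper bound on selection. In 100,000 simulated trials (normal data, no true effect, pooled one-sided t-test at 0.05), the chance of a significant PP result was:

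| Membership | 37:12 | 19:6 |
|---|---|---|
| Fixed blind | 5.0% | 5.1% |
| Free to drop the single most helpful patient | 11.4% | 13.2% |
| Free to drop up to one per arm | 16.6% | 19.9% |

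Step 4 supposes deliberate choice by result and uses a t-test instead of the repeated-measures model. It bounds what the timing rule permits and is not evidence of misuse.

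**The case against.** The best defence has four parts.

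- **SAP 6 may already cover the ratings.** SAP 16.1 uses the term database lock for the Week 16 event. If SAP 6 means the same one, deviations up to Week 16 are rated before unblinding. A reader might infer that the ratings, like the PP set, can wait until the final analysis; the text does not say that. It leaves two locks and names neither. This part stands as far as the ratings go. It does not rescue the PP set, whose deadline is stated and is later.
- **Most of PP membership is rule-based, and the unseen deviation plan may define major violations and who rates them.** True, so the room for discretion is unknown and may be small. But SAP 6 cites that plan for categories, not for the timing of PP approval. The compliance cut may also remove few patients: SAP 8 pools study tablets with NA tablets, so a patient taking all 112 NA tablets and no study tablets over 112 days scores 112/224 = 50%, which is not below 50%.
- **Work starts earlier.** The disposition table, with a PP row, is planned for both DSMC meetings, and the population and deviation listings for the futility meeting. Rating is therefore likely to begin before Week 16. Those outputs precede Week 16 for some patients, so PP status in them can only be provisional.
- **The order in SAP 16.2 shows good intent.** Populations are listed as approved before unblinding. That is a fair reading, but the order was not adapted to the unblinding added in SAP 16.1.

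A reader might also infer that the primary result is exposed, or that the sponsor plans to choose exclusions unblinded. Neither is supported. No PP decision can alter the ITT analysis, and the documents do not say who approves the PP set.

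**Conclusion.** The gap holds for the judgement-based part of PP membership at Week 16: the stated deadline allows it to be settled after arm and outcome are known. For the deviation ratings the position is undetermined, because SAP 6 does not identify its lock. Protocol 11.2.3 is not at fault by itself; the conflict arises from the unblinding that SAP 16.1 adds.

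The consequence is moderate. It touches two sensitivity runs, and one contestable placebo exclusion of the kind illustrated moves the estimate by less than half a standard error, more at the reduced sample size than at the planned one. The conclusion about timing rests on the SAP text alone. The size rests on the planning SD, an assumed 19:6 split and an arbitrary 1 SD patient. It merits correction because the remedy is cheap and the PP runs lose much of their purpose without it.

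**What to change.** Amend three SAP sections.

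- **SAP 6:** name the lock. All deviations up to Week 16 are to be rated by blinded medical monitors before the Week 16 unblinding, and the SAP should state how the Important status relates to a major protocol violation.
- **SAP 4.1.6:** PP membership for the Week 16 primary endpoint is approved and signed off, blinded, before that unblinding.
- **SAP 16.2:** align the order of population approval and unblinding with SAP 16.1. Any later change to the Week 16 PP set is recorded as made after unblinding, with the reason.

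The cost is a few sentences and one blinded data-review meeting held earlier; no further data are needed. If the unblinding has already happened, the study report should say when the PP set was fixed, by whom, and whether they then had access to the treatment codes.

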5. PARTICIPANT DISPOSITION AND ANALYSIS POPULATIONS

Participant disposition and analysis population analysis will be based on the ITT population. Participant disposition and analysis populations will be summarized descriptively as described in section 3.1 (categorical descriptive analysis).

5.1.1 Participant Disposition

Participant disposition will include the number of participants who completed the study as planned, participants withdrawn from the study, as well as the primary reason for early termination. Participant disposition will be summarized descriptively.

A listing of patient disposition with study discontinuation and treatment discontinuation will be presented. Whether a patient had any ongoing AEs, the date of last dose (EYP001a/Placebo and NA), reason for treatment discontinuation (if applicable), date of last contact (or date of death) and date of withdrawal of consent (if applicable) will be included.

Screening failures and reason for screening failure, will be noted in the listing of eligibility criteria. All withdrawals from the study, taking place on or after study drug administration, will be fully documented in the body of the clinical study report (CSR).

5.1.2 Analysis Populations

The number of participants included in each study populations will be summarized descriptively.

In addition, the inclusion of each participant into/from each of the defined analysis populations will be presented in the by-participant data listings.

6. PROTOCOL DEVIATIONS

Protocol deviations will be presented for each participant in the by-participant data listings for the enrolled set. All data will be listed by treatment group.

Prior to database lock, all protocol deviations will be reviewed by medical monitors and assigned a status of Important if qualifying as such.

Protocol deviations and important protocol deviations will be categorized as noted in the Protocol Deviation Management Plan Version 1.0 dated 2020-01-13.

7. DEMOGRAPHIC AND BASELINE INFORMATION

Demographic and baseline information analysis will be based on the ITT population. Summary tables may be repeated for the mITT, Safety and PP analysis sets if different from the ITT analysis set. Demographic and baseline information will be summarized descriptively as described in section 3.1.

7.1 Demographics

The following demographic parameters will be analyzed:

Continuous descriptive analysis:

- Age (years)
- Height (cm)
- Weight (kg)
- BMI (kg/m²)
- Audit-C overall score

Categorical descriptive analysis:

- Sex
- Childbearing Potential
- Race
- Ethnicity
- HBV Genotype
- HBeAg Status (Positive/Negative)

7.2 Medical history

Medical / Surgical history will be coded using MedDRA® currently in effect at Novotech at the time of database lock. and will be presented in the by-participant data listings.

7.3 Viral Serology

Hepatitis D virus (anti-HDV), antibody to HIV (anti-HIV), antibody to HCV (anti-HCV), quantitative HBsAg, anti-HBs, Anti-HBe, a PCR-based quantitative HCV viral load (for positive HCV antibody-test results only), will be presented in the by-participant data listings.

The viral serology result will be summarized at baseline visit by treatment group.

7.4 Drugs of Abuse

Drugs of abuse results will be presented in the by-participant data listings.

8. TREATMENT EXPOSURE AND COMPLIANCE

EYP001a/Placebo administration information (study drug administered (Yes/No), reason for non-administration date and time of administration, reason for dose adjustment and adjusted dose administered will be listed by treatment group. Patient fasting listed will also be noted.

For NA, treatment administered, reason not administered, date and time of administration, dose taken per protocol (Yes/No), reason for dose adjustment and adjusted dose administered will be listed by treatment group. NA switching during the screening period will also be listed.

Missed doses and reason for missed doses along with corresponding AEs will be listed as well.

EYP001a/Placebo and NA accountability will be listed by treatment group. The following fields will be included: number of 200mg tablets dispensed, date dispensed, number of 200mg tablets used, date returned, doses missed (Yes/No), patient compliant (Yes/No), if no reason not compliant and the percentage of treatment compliance.

Treatment Compliance is defined as:

$$\left(\frac{\text{Total Drug Administered}}{\text{Expected Drug Administered}} \right) * 100$$

The total drug administered is defined as:

(Number of 200mg Tablets Used + Number of NA Tablets Used during treatment period)

The expected drug administered is defined as:

The expected drug administered for EYP001a/Placebo + The expected drug administered for NA during treatment period

- The expected drug administered for EYP001a/Placebo is defined as:

Number of treatment days for EYP001a/Placebo × daily dosage (= 1 tablet), where the number of treatment days for EYP001a/Placebo will be calculated as:

Number of treatment Day = (Date of treatment visit 1 - Date of last treatment visit) +1 during treatment period.

- The expected drug administered for NA is defined as:

Number of treatment days for NA × daily dosage (= 1 tablet), where the number of treatment days for NA will be calculated as:

Number of treatment Day = (Date of treatment visit 1 - Date of last treatment visit) +1 during treatment period.

Treatment compliance (including count and percentage with <50% compliance, >=50% and =< 80%, and > 80% compliance) will be summarized descriptively as described in section 3.1(categorical descriptive analysis) under Safety analysis set.

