#### 4.6. Stopping Rules

Dosing for a patient will be discontinued for any of the following events:

1. One occurrence of an SAE assessed to be definitely, probably or possibly related to dosing with the study drug.
2. One occurrence of a Grade 4 AE (i.e. life-threatening) assessed to be considered “possibly related” or “probably related” to the study drug
3. One occurrence a Grade 3 rash or higher or acute systemic allergic reaction.
4. Confirmation of any of the study drug discontinuation criteria as described in [Section 8.3](#).
5. Occurrence of any condition that, in the opinion of the Investigator, significantly jeopardizes the wellbeing and safety of the patient and is assessed to be probably related to dosing with the study drug.
6. Clinically significant changes in vital signs or ECGs (such as arrhythmias) assessed to be considered “possibly related” or “probably related” to the study drug (i.e., no alternative explanation likely).
7. Clinically significant changes in the safety laboratory tests assessed to be considered “probably related” to the study drug (i.e., no alternative explanation likely).
8. A subject experiences a breakthrough (defined by quantifiable HBV DNA increase of  $\geq 1 \log_{10}$  HBV DNA copies/mL above LLOQ) the subject should return to the study site for a confirmatory measurement within two weeks, and if virologic breakthrough is confirmed, EYP001a or placebo dosing should be stopped and NA treatment should be continued or modified at the investigator’s discretion.

If two or more patients meet study drug stopping criteria #1, or #3 to #8, recruitment and dosing should be suspended or terminated for the remaining patients, pending the outcome of a DSMC review. The DSMC must review all safety data and provide clearance prior to dosing any additional patients.

If one patient meets study drug stopping criteria #2, recruitment and dosing should be suspended or terminated for the remaining patients, pending the outcome of a DSMC review.

If one patient experiences a Grade 5 common terminology criteria for adverse event (CTCAE) toxicity (based on CTCAE, version 5.0), or if more than 2 patients develop a Grade 3 CTCAE toxicity in the same category, the study will be paused, and safety reports

will be submitted to the DSMC for review and clearance prior to dosing any additional patients.

In other situations, re-initiation of study drug may be considered after consultation with the Medical Monitor.

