### **5.11. Treatment Compliance**

The study drug (EYP001a/Placebo and NA) will be dispensed to the patients by the Investigator or study site personnel dedicated to the study on the treatment visits 1, 3, 5, 7 and 9 (for EYP001a/Placebo dispensation is only at visits 1 and 5, as each boxe is for 8 weeks of treatment). Please note 16 weeks of treatment (EYP001a/Placebo and NA) with 8 weeks treatment units will be dispensed. Should the patient "loose" treatment units the check on sufficient treatment can be made at each fortnightly visit. Patient diary will be provided on the treatment visits 1, 2, 3, 4, 5, 6, 7, 8 and 9. NA will also be dispensed along with patient diary, on the follow up visits 1 and 2. Patients will administer the study drug (EYP001a/placebo and NA) outside the study sites (at home) during the treatment period (Week 1 to Week 16) and follow-up period (Week 17 to Week 40) as instructed by Investigator or study-site personnel and will record the dosing details in the patient diary to document compliance.

Data pertaining to tablet count for the study drug will be collected on the treatment visits 2, 3, 4, 5, 6, 7, 8 and 9; on all follow-up visits and on ET visit. If a patient's drug administration and site-related procedures are not conducted as defined in the protocol, the Investigator will make note of ensuring compliance to the protocol for future activities.

The date and time of each study drug administration and accompanying activity recorded in the patient diary will be transcribed in the eCRF. Detailed instructions for the dispensing instructions of EYP001a are described in the study pharmacy manual.

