2. PROJECT OVERVIEW

2.1 Study Design

This is a prospective, multi-centre, international randomized, double-blind, placebo controlled, Phase 2a experimental study of oral FXR modulator EYP001a/placebo combined with Nucleos(t)ide analogues (NA) in virologically suppressed CHB patients to improve functional cure rates.

In total 49 eligible patients will be enrolled and randomized at approximately 14 study sites in 4 countries. Patients will be randomized prior to study drug (EYP001a or placebo and NA) administration on Day 1 in the ratio of 3:1 into 2 arms:

[figure not shown]
- Experimental Arm: EYP001a 200 mg once daily (QD) + NA daily (37 patients)
- Control Arm: Placebo + NA daily (12 patients)

Patients will also be stratified per HBeAg status, based on medical history HBeAg value or established during screening, to obtain a balanced randomization to both study arms.

The maximum total engagement duration for eligible patients in this study is up to 370 days: 90 days screening, 112 days (16 weeks) experimental treatment period and 168 days (24 weeks) follow-up on NA standard of care therapy (SOC) only.

Patients enrolled in the study will be assessed as outpatients. Patient screening will occur no more than 90 days prior to the Day 1 visit. Eligible patients will undergo further assessments on Day 1 to qualify for study drug administration on Day 1.

Figure 1: Study Design

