13.1 Adverse Events

All AEs including will be coded using MedDRA. All AE summaries will be restricted to TEAEs only. Summary tables will include the number of participants (%) experiencing an event and the number of events. Participants will be counted only once for each SOC and PT level (categorical descriptive analysis).

AE and SAE will be analysed taking into account any identified subject with Sars-Cov2 infection during and post-pandemic measures phases. Such an analysis will be operated through the independent Data Monitoring Committee (DMC).

The TEAE summaries will include:

- Overall summary of TEAEs.
 - Number of TEAEs
 - Number of TEAEs with Severity \geq Grade 3 Severe
 - Number of Serious TEAEs
 - Number of Study Drug Related TEAEs (Drug Related: A Possibly, Probably or Definitely related TEAE)
 - Number of Entecavir (ETV) Related TEAEs (Drug Related: A Possibly, Probably or Definitely related TEAE)
 - Number of Tenofovir Disoproxil Fumarate (TDF) Related TEAEs (Drug Related: A Possibly, Probably or Definitely related TEAE)
 - Number of TEAEs leading to study drug withdrawal
- TEAE summary by SOC and PT.
- TEAE summary of serious events by SOC and PT.
- TEAE summary by SOC, PT and Severity.
- TEAE summary by SOC, PT and relationship to study drug.
- TEAE summary by SOC, PT and relationship to ETV.
- TEAE summary by SOC, PT and relationship to TD.
- TEAE summary of events leading to the study drug discontinuation by SOC and PT.

All AEs will be listed and will include verbatim term, PT, SOC, treatment, causality to study drug, ETV and TDF, severity, seriousness, outcome, and action taken with regards to the study drug and AE. Separate listings will be created for SAEs and events leading to study drug withdrawal.

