Subject ID	Class/Preferred Term	Start Date/Time (YYYY-MM-DD/HH:MM)	End Date/Time (YYYY-MM-DD/HH:MM)	SAE Criteria	TEAE Severity	Relationship to Study Drug/ETV/TD	Action Taken for AE	Concomitant Medication	Action Taken for Study treatment	Outcome
XXX	XXXXXXXXXXXXXXXXXXXX ZZZZZZZZZZZZZZZZZZZZ YYYYYYYYYYYYYYYYYYY	YYYY-MM-DD/ HH:MM	YYYY-MM-DD/ HH:MM	Life Threatening	Yes Mild	Related/Unlikely/Possibly Related	Medication required	XXXXXX	Dose Not Changed	Recovered/ Resolved
XXX	XXXXXXXXXXXXXXXXXXXX ZZZZZZZZZZZZZZZZZZZZ YYYYYYYYYYYYYYYYYYY	YYYY-MM-DD/ HH:MM	Ongoing	Congenital Anomaly or Birth Defect	Yes No Moderate	Related/Unlikely/Possibly Related	None		N/A	Recovering / Resolving
...										

SAE = Serious Adverse Event. TEAE = A treatment-emergent adverse event. ETV = Entecavir. TD = Tenofovir Disoproxil.

Medical Dictionary for Regulatory Activities (MedDRA) Version xx.x

Listing 16.2.7.3 Adverse Events Leading to Study Drug Withdrawal (ITT Set)

Group 1: EYP001a 200 mg QD + NA daily

Subject ID	Adverse Event Verbatim/ System Organ Class/ Preferred Term	Start Date/Time End Date/Time (YYYY-MM-DD/ HH:MM)	SAE	TEAE	Severity	Relationship to Study Drug/ETV/TD	Action Taken for AE	Concomitant Medication	Action Taken for Study treatment	Outcome
XXX	XXXXXXXXXXXXXXXXXXXX ZZZZZZZZZZZZZZZZZZZZ YYYYYYYYYYYYYYYYYYYY	YYYY-MM-DD/ HH:MM YYYY-MM-DD/ HH:MM	Yes	Yes	Mild	Related/Unlikely/Possibly Related	Medication required	XXXXXX	Dose Not Changed	Recovered/ Resolved
XXX	XXXXXXXXXXXXXXXXXXXX ZZZZZZZZZZZZZZZZZZZZ YYYYYYYYYYYYYYYYYYYY	YYYY-MM-DD/ HH:MM Ongoing	Yes	No	Moderate	Related/Unlikely/Possibly Related	None		N/A	Recovering / Resolving
...										

SAE = Serious Adverse Event. TEAE = A treatment-emergent adverse event. ETV = Entecavir. TD = Tenofovir Disoproxil.

Medical Dictionary for Regulatory Activities (MedDRA) Version xx.x

Programming Note:

- Select action taken for EYO001a/Placebo = "Drug Withdrawn".

Listing 16.2.8.1.1 Hematology and Coagulation (ITT Set)

Group 1: EYP001a 200 mg QD + NA daily

Parameter: Hemoglobin (unit)

Subject ID	Visit	Collection Date/ Time (YYYY-MM-DD/ HH:MM)	Actual Value	Change from Baseline [1]	High/Low Flag	Clinically Significant	Comments
XXX	Screening	YYYY-MM-DD/ HH:MM	xx	N/A			
	Day 1 [1]	YYYY-MM-DD/ HH:MM	xx	N/A	H	NCS	xxxxxxxx
	Week 2	YYYY-MM-DD/ HH:MM	xx	xx			
	Week 4	YYYY-MM-DD/ HH:MM	xx	xx	H		
	Week 6	YYYY-MM-DD/ HH:MM	xx	xx			
...	Etc.	YYYY-MM-DD/ HH:MM	xx	xx			

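### The only compliance percentage in SAP 8 pools EYP001a/placebo with NA tablets, so a 50% per-protocol cut based on it can keep patients who took little of the randomised product

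*SAP*

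**What the plan says.** SAP section 8 gives a single formula for treatment compliance: total drug taken over expected drug, times 100. The total is "Number of 200mg Tablets Used + Number of NA Tablets Used during treatment period". The expected amount is the sum of one EYP001a/placebo tablet per day and one NA tablet per day over the treatment period. Expected counts are written out for each product, but no percentage is defined for either alone. Table 14.1.4 reports the pooled percentage in three bands (<50%, 50% to 80%, >80%).

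SAP 4.1.6 adds to the PP definition that "patients with the study drug compliance of <50% will be excluded". It does not say which product is meant and does not refer to section 8.

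The term *study drug* is used in two ways:

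- **Both products.** SAP 2.1: "Patients will be randomized prior to study drug (EYP001a or placebo and NA) administration on Day 1". Protocol 5.11, the compliance section: "The study drug (EYP001a/Placebo and NA) will be dispensed to the patients by the Investigator".
- **EYP001a/placebo alone.** SAP 13.1 plans a "TEAE summary by SOC, PT and relationship to study drug" alongside separate summaries for entecavir and tenofovir. The programming note to Listing 16.2.7.3, on withdrawal from study drug, reads "Select action taken for EYO001a/Placebo".

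**The concern.** NA is background therapy in both arms; EYP001a/placebo is what was randomised. A PP set meant to support the primary endpoint should remove patients who did not take the randomised product. A percentage that averages the two products cannot do this reliably, because good NA intake offsets poor EYP001a/placebo intake, and the reverse.

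Good NA intake is a reasonable expectation: Protocol 4.2 requires at least 12 months of stable NA therapy and HBV DNA below the LLOQ. This is an inference, since no adherence figures are given. Protocol 4.6 rule 8 documents one route to high NA with low EYP001a/placebo intake. After a confirmed virologic breakthrough, "EYP001a or placebo dosing should be stopped and NA treatment should be continued or modified".

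If 4.1.6 instead means EYP001a/placebo alone, the rule targets the right product, but the SAP never writes down that percentage. Both readings need a correction.

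Table 14.1.4 is affected too. SAP section 18 flags it for both DSMC meetings. Exposure (Listing 16.2.5.2) and missed doses (Listing 16.2.5.4) separate the products, but SAP section 19 flags these only for the safety and futility meeting. The tablet counts by product (Listing 16.2.5.3) are flagged for neither.

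**Working it through.** The plan gives no worked compliance figure to reproduce, so the check applies the section 8 formula directly.

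**Inputs.** One tablet per day for each product (SAP 8); 112 treatment days (SAP 2.1); PP threshold <50% (SAP 4.1.6). The NA levels below are assumptions shown as a range. The day count is taken in the evidently intended order, last visit minus first visit plus 1 = 112. The order printed in section 8 is reversed and would give (1 − 112) + 1 = −110.

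**Formula.** Let *e* be EYP001a/placebo tablets and *n* be NA tablets taken.

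Pooled compliance = 100 × (*e* + *n*) / (112 + 112) = 100 × (*e* + *n*) / 224

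This is the simple mean of the two product percentages. It is below 50% only if *e* + *n* < 112. A cut on EYP001a/placebo alone would exclude *e* < 56, that is 0 to 55 tablets.

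**Full NA intake (*n* = 112).**

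- *e* = 0: 112/224 = 50.0%, kept
- *e* = 28 (25%): 140/224 = 62.5%, kept
- *e* = 55 (49.1%): 167/224 = 74.6%, kept
- *e* = 67: 179/224 = 79.9%, middle band of Table 14.1.4
- *e* = 68 (60.7%): 180/224 = 80.4%, in the >80% band

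**Range of NA intake.**

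| NA tablets *n* | Pooled cut excludes *e* | Of the 56 counts with *e* = 0 to 55, kept | Counts with *e* ≥ 56 excluded |
|---|---|---|---|
| 112 (100%) | none | 56 | 0 |
| 101 (90%) | 0–10 | 45 | 0 |
| 90 (80%) | 0–21 | 34 | 0 |
| 84 (75%) | 0–27 | 28 | 0 |
| 56 (50%) | 0–55 | 0 | 0 |
| 28 (25%) | 0–83 | 0 | 28 (56–83) |

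The two cuts agree only when NA intake is 50%. Above that, the pooled cut keeps patients below half on EYP001a/placebo. Below it, the pooled cut removes patients above half: at *n* = 28, 83 tablets (74% of 112) score 111/224 = 49.6%. These are possible tablet counts, not numbers of patients.

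**Early stop of EYP001a/placebo.** Take 28 tablets by Day 28, with NA to Day 112. If both day counts run to Day 112, the pooled score is 140/224 = 62.5%. If the EYP001a/placebo count ends at Day 28, it is 140/(28 + 112) = 100%. Neither is below 50%. Section 8 does not define the last treatment visit for such a patient, so the answer depends on the programmer.

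**The case against.** The strongest reply is that the harm is conditional. SAP 4.1.6 does not cite section 8, and SAP 13.1 and Listing 16.2.7.3 use *study drug* for the randomised product. Section 8 also states both parts of an EYP001a/placebo-only percentage, so only the ratio is missing. This is fair, and it makes the repair cheap. But the pooled value is the only percentage defined, its lowest band is the same <50%, and SAP 2.1 and Protocol 5.11 support the pooled reading.

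Second, other rules may remove these patients. PP members must meet the mITT definition and so "have a measurable baseline HBsAg assessment and a 16-week post baseline efficacy assessment"; major protocol violations are excluded; and Protocol 4.7 allows discontinuation for non-compliance. These may catch some. However, a patient who stops EYP001a/placebo and attends Week 16 can still qualify for mITT, and the Protocol Deviation Management Plan is not among the documents. An explicit adherence threshold should work by itself.

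Third, in the rule 8 case separate percentages alone may not help: if the day count ends at the stop, EYP001a/placebo compliance is 28/28 = 100%. This stands, and it is why the last treatment visit must also be defined. Rule 8 stopping is also protocol-directed and not poor adherence.

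Fourth, the DSMC sees other outputs at both meetings, including disposition, adverse events leading to discontinuation and stopping-rule listings, and no futility or stopping rule uses the compliance percentage. This is correct and limits the DSMC point. Those outputs still do not show how much EYP001a/placebo was taken.

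**Conclusion.** The concern holds in its conditional form. Used as written, the section 8 percentage gives a PP cut and a Table 14.1.4 that do not measure adherence to the product under test. With full NA intake the cut excludes no one; with NA at 90% it reaches only patients with 10 or fewer of 112 EYP001a/placebo tablets.

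The reach is limited. The primary analysis is on the ITT set and is unaffected; PP is supportive and Table 14.1.4 is descriptive. How many patients would be misclassified cannot be known from the documents. The sets are small, though. SAP section 15 reports enrolment suspended after about 25 randomisations, which at 3:1 is about 19 and 6 patients (25 × 3/4 = 18.75; 25 × 1/4 = 6.25). One misclassified patient is then about 5% (1/19) or 17% (1/6) of an arm.

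The tablet figures assume 112 days for each product, the corrected date order, and the NA levels shown. The point should be fixed, but it does not threaten the primary result.

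**What to change.** Before unblinding, amend the SAP as follows:

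1. In section 8, define compliance separately for EYP001a/placebo and for NA.
2. In 4.1.6, state that the <50% exclusion uses EYP001a/placebo compliance, and say whether an NA threshold also applies.
3. In Table 14.1.4, show the bands for each product.
4. In section 8, define the last treatment visit for a patient who stops EYP001a/placebo but continues NA, since the denominator depends on it.

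As a separate minor correction, reverse the date subtraction in section 8 to last treatment visit minus treatment visit 1, plus 1.

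Timing matters because SAP 16.1 plans to unblind all patients after the Week 16 database lock, whereas 4.1.6 only requires the PP set to be identified before the final analysis. A formula chosen between those two points would be open to challenge as data-driven.

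The cost is a few lines in 4.1.6 and 8 and one extra block in Table 14.1.4. No new data are needed: Listing 16.2.5.3 already holds tablet counts and compliance flags separately by product.
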